 Other Locations, Specify: (Specify location(s)):	 International Research Site

c. Additional Required Documents (check all that apply):

 *YCCI-Scientific and Safety Committee (YCCI-SSC)	 N/A
 *Pediatric Protocol Review Committee (PPRC)	Approval Date:
 *YCC Protocol Review Committee (YRC-PRC)	Approval Date:
 *Dept. of Veterans Affairs, West Haven VA HSS	Approval Date:
 *Radioactive Drug Research Committee (RDRC)	Approval Date:
 YNHH-Radiation Safety Committee (YNHH-RSC)	Approval Date: Pending
 Yale University RSC (YU-RSC)	Approval Date:
 Magnetic Resonance Research Center PRC (MRRC-PRC)	Approval Date:
 *Nursing Research Committee	Approval Date:
 YSM/YNHH Cancer Data Repository (CaDR)	Approval Date:
 Dept. of Lab Medicine request for services or specimens form	
 Imaging on YNHH Diagnostic Radiology equipment request form (YDRCTO request) found at http://radiology.yale.edu/research/ClinTrials.aspx	

**Approval from these committees is required before final HIC approval is granted. See instructions for documents required for initial submission and approval of the protocol. Allow sufficient time for these requests. Check with the oversight body for their time requirements.*

2. **Probable Duration of Project:** State the expected duration of the project, including all follow-up and data analysis activities.

1 Year.

3. **Research Type/Phase: (Check all that apply)**

a. **Study Type**

Single Center Study
 Multi-Center Study

Does the Yale PI serve as the PI of the multi-site study? Yes No

Coordinating Center/Data Management
 Other:

➤ *List of the other sites:*

[name]

Cleveland Clinic, [name]

[name]

Brigham and Women's Hospital, [name]

[name]

University of Miami Health System, [name]

[name] Sr.

Duke University Hospital, [name]

[name]

Cooper University Hospital, [name]

[name]

United Hospital, [name]

[name]

Carolinas HealthCare System, [name]

b. Study Phase	 N/A			

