7. Using fluoroscopic guidance, properly inflate the balloon with 20/80 contrast/saline mix using the recommended 60cc syringe until the balloon conforms to the vasculature.
8. Record the time to balloon deployment (i.e. complete conformance of the balloon to the vasculature based on fluoroscopy).
9. Use fluoroscopy and cine to confirm and record the position of the balloon.
10. Record vital signs (HR, BP, SPO2) post balloon inflation but prior to contrast injection.

11. Inject contrast from superior venous access and record cine to assess occlusion of the SVC.
12. Allow one repositioning of balloon if occlusion not obtained and record additional cine to reassess occlusion of SVC.
13. Record vital signs (HR, BP, SPO2) 1 min after occlusion has been confirmed.
14. Deflate the balloon fully using the 60cc syringe and remove the balloon from the body. Leave guidewire and femoral sheath in place (can be used to deliver a bridge balloon catheter in case if SVC tear occurred during the extraction procedure – this is a clinical indication and is not an investigational part). Repeat venogram after balloon deflation and removal to document SVC area post occlusion.
15. Record vital signs (HR, BP, SPO2) and ABG 5,10,15,20,25, and 30 minutes post balloon deflation.
16. Record all vital signs (HR,BP,SPO2) that is out of the expected range for the patient within 30 minutes post balloon deflation.
17. Continue with the lead extraction procedure.

The extraction procedure itself is a standard of care procedure, it is clinically indicated in the targeted patient population. The deployment and use of the Balloon Bridge is a research related activity, will be done for the research purposes only.

All the procedures pertaining to lead extraction is standard of care and routinely used. The research portion of the study will consist of balloon inflation prior to initiation of the lead extraction procedure. There will be no control group for this study. The device itself will be provided at no cost.

This study will evaluate the use of the Bridge occlusion balloon in 3-5 lead extraction patients scheduled for lead extraction (patients indicated for lead extraction). This study will be performed prior to lead extraction in an intact SVC without prior SVC occlusion.

The following data will be collected:

- Cine at baseline and after removal of the Bridge occlusion balloon.
- Cine of the insertion/positioning/inflation of the Bridge occlusion balloon.

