Mechanism for registering each subject at Yale:

- Each subject has two different registration codes;
 - ✓ First ID: is done by each site which includes the site ID (2digits) and subject ID (3 digits) e.g. [XX-XXX] - This will allow us to know the enrolling site and enrollment order of each subject.
 - ✓ Second ID: is done here at Yale based on the order of receiving the data collection form e.g. [XXX]

Mechanism for routine communication with site investigators:

- The PI will send a weekly mass e-mail for the site investigators to discuss the study progress.
- A copy of the email communication will be kept in the regulatory binder.

Plan to ensure ongoing IRB approval at all sites and approval of any amendments:

- Based on the IRB approvals tracking system, 1st email reminder will be sent 3 months before study expiration date as a reminder of study reapproval. Follow up emails each week until a documentation of IRB submission is received.
- All sites are required to update the central site with any amendments submissions and a copy of the approval will be saved in the regulatory binder.

4. Genetic Testing N/A

5. Subject Population: Provide a detailed description of the types of human subjects who will be recruited into this study.

Patients indicated for lead extraction. 5 patients per site can be tested as part of this study.

6. Subject classification: Check off all classifications of subjects that will be specifically recruited for enrollment in the research project. Will subjects who may require additional safeguards or other considerations be enrolled in the study? If so, identify the population of subjects requiring special safeguards and provide a justification for their involvement.

 Children	 Healthy	 Fetal material, placenta, or dead fetus
 Non-English Speaking	 Prisoners	 Economically disadvantaged persons
 Decisionally Impaired	 Employees	 Pregnant women and/or fetuses
 Yale Students	 Females of childbearing potential	

NOTE: Is this research proposal designed to enroll children who are wards of the state as potential subjects? Yes No (If yes, see Instructions section VII #4 for further requirements)

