 - **The PI and investigators will review the data quarterly for safety issues. No statistical claims are being made with the data being collected, and there is no minimum**

•

- **sample size required.**
 - iii. What will the multi-site process be for protocol modifications?
 - **The PI will request any protocol modifications to be applied to all sites. Protocol amendment will be requested with the need of local IRB acknowledgements to be collected from all sites.**
 - **All the IRB related documentations are kept in the master regulatory binder in the research office. Copies of the PIs curriculum vitae and qualifications are kept in the regulatory binder.**
 - **All sites are required to send their IRB approvals to the central site.**

12. Statistical Considerations: Describe the statistical analyses that support the study design.

A sample size of 3-5 patients per site was selected to allow for a sufficient physician experience to generate an ease of use and efficacy of occlusion determination (target 25 total)
No statistical claims are being made with the data being collected, there is no minimum sample size required.

SECTION VI: RESEARCH INVOLVING DRUGS, BIOLOGICS, RADIOTRACERS, PLACEBOS AND DEVICES

If this section (or one of its parts, A or B) is not applicable, state N/A and delete the rest of the section.

A. DRUGS, BIOLOGICS and RADIOTRACERS N/A

B. DEVICES

1. Are there any investigational devices used or investigational procedures performed at Yale-New Haven Hospital (YNHH) (e.g., in the YNHH Operating Room or YNHH Heart and Vascular Center)? Yes No *If Yes, please be aware of the following requirements:*
 - a. A YNHH New Product/Trial Request Form must be completed via EPIC: **Pull down the Tools tab in the EPIC Banner, Click on Lawson, Click on “Add new” under the New Technology Request Summary and fill out the forms requested including the “Initial**

Request Form,” “Clinical Evidence Summary, “ and attach any other pertinent documents. Then select “save and submit” to submit your request; and

b. Your request must be reviewed and approved **in writing** by the appropriate YNHH committee before patients/subjects may be scheduled to receive the investigational device or investigational procedure.

2. What is the name of the device to be studied in this protocol?

Bridge Occlusion Balloon Catheter.

Has this device been FDA approved? Yes No
If yes, state for what indication.

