- a. targeted for enrollment at Yale for this protocol 5
- b. If this is a multi-site study, give the total number of subjects targeted across all sites 25 (8 sites including Yale)

2. Indicate recruitment methods below. Attach copies of any recruitment materials that will be used.

 Flyers	 Internet/Web Postings	 Radio
 Posters	 Mass E-mail Solicitation	 Telephone
 Letter	 Departmental/Center Website	 Television
 Medical Record Review	 Departmental/Center Research Boards	 Newspaper
 Departmental/Center Newsletters	 Web-Based Clinical Trial Registries	
 YCCI Recruitment database	 Clinicaltrials.gov Registry (do not send materials to HIC)	
 Other (describe): Patients who are already scheduled for elective lead extraction.		

3. Recruitment Procedures:

- a. Describe how potential subjects will be identified.

The patients will be identified through the clinic evaluation and the EP schedule.

Patients who are eligible or scheduled for Lead Extraction will be approached to participate in the study. The investigators will review the patients' charts and they will determine eligible patients based on inclusion and exclusion criteria.

- b. Describe how potential subjects are contacted.

The patients will be approached by the study team in the clinic or before the procedure to explain the study and to answer any questions.

- c. Who is recruiting potential subjects?

All the investigators will be involved in recruiting potential subjects

4. Screening Procedures

- a. Will email or telephone correspondence be used to screen potential subjects for eligibility prior to the potential subject coming to the research office? Yes No
- b. If yes, identify below all health information to be collected as part of screening and check off any of the following HIPAA identifiers to be collected and retained by the research team during this screening process.

HEALTH INFORMATION TO BE COLLECTED:**HIPAA identifiers:**

- Names

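### Do the enrolment figures (25 in total, 8 sites, Yale 5, 3-5 per site) contradict one another in a way that matters?

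*Protocol*

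**What the plan says.** Five places in the protocol bear on the number of patients.

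- Section II.3.a, under "List of the other sites", names seven centres besides Yale.
- Section V.3 (Research Plan): "This study will evaluate the use of the Bridge occlusion balloon in 3-5 lead extraction patients scheduled for lead extraction". The words 'per site' do not appear.
- Section V.5 (Subject Population): "5 patients per site can be tested as part of this study".
- Section V.12 (Statistical Considerations): "A sample size of 3-5 patients per site was selected to allow for a sufficient physician experience", with the purpose given as "ease of use and efficacy of occlusion determination (target 25 total". The next sentence disclaims statistical claims and says that no minimum sample size is required. The interim-results item of Section V.11.d says the same.
- Section VII.1 (Targeted Enrollment): item a reads "targeted for enrollment at Yale for this protocol 5", and item b reads "give the total number of subjects targeted across all sites 25 (8 sites including Yale".

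Two further provisions depend on counts of patients. In Section V.11 the study monitor looks at additional subjects once a site has enrolled its third, and the data monitoring committee reviews all data once half of the subjects are in.

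**The concern.** Read side by side as exact numbers, the figures cannot all hold. If every site is to enrol at least 3 and Yale is to enrol 5, the total must be at least 26, yet 25 is stated. With Yale at 5 and the total at 25, some other site must stop at 2 or fewer. That site would miss the physician experience that Section V.12 gives as the only reason for the sample size, and it would never trigger the monitor's third-subject look.

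The Research Plan, taken literally, describes a study of 3-5 patients in all, a fifth or less of the total given elsewhere. The allowance of 5 per site, multiplied by eight sites, would admit 40.

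The balloon inflation is done for research only, offers subjects no direct benefit and is rated as more than minimal risk. A reader may therefore fairly ask for an unambiguous number of exposed patients, and for a half-way review that does not move.

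**Working it through.** **Inputs.** Sites: 8 (Section VII.1.b), which agrees with Yale plus the seven listed in Section II.3.a. Yale target: 5 (VII.1.a). Per-site range: 3 to 5 (V.12). Total target: 25 (V.12 and VII.1.b). Per-site allowance: 5 (V.5). No power formula applies, because there is no control group and no statistical claim.

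**The plan's own total.** Sites × per-site range: 8 × 3 = 24 and 8 × 5 = 40. The stated 25 lies within 24 to 40, and 25 / 8 = 3.1 per site lies within 3 to 5. So the total and the per-site range in Section V.12 agree with each other.

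**Adding Yale's 5.** Yale + 7 × lower end of range = 5 + 7 × 3 = 26. This exceeds 25 by 1, and 1 / 25 = 4%. Equivalently, (25 − 5) / 7 = 20 / 7 = 2.86 per other site, against a lower end of 3.

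**Is any exact split possible?** Eight sites at 3 use 24 patients and leave one over, so the only split of 25 with every site at 3 to 5 is seven sites at 3 and one at 4. No site can then have 5. If 3 is a floor and Yale must reach 5, the figures are infeasible by one patient. With Yale at 5 and the floor dropped, the smallest departure is one site at 2: 5 + 6 × 3 + 2 = 25.

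**The allowance.** 8 × 5 = 40, and 40 − 25 = 15, or 60% above target. This needs every site to fill its allowance and the stated total to be disregarded.

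**The half-way review.** 25 / 2 = 12.5, so the 13th subject; 26 / 2 = 13, again the 13th. Only a total of 40 would move it, to the 20th.

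**The Research Plan wording.** A whole-study size of 3-5 cannot be meant: Yale alone is allotted 5 and there are seven other sites. The same 3-5 range appears in Section V.12 with 'per site' attached. The only reading consistent with the rest of the protocol is that these words were left out.

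**The case for a change.** The strongest case for a change is that these are whole-number site counts, with no rounding to excuse a difference of one. Yale at 5, at least 3 elsewhere and 25 in all are jointly impossible, and the per-site experience is the only justification offered for the size. Nothing calls 25 a cap, and the number of patients exposed to a research-only procedure of more than minimal risk ought to be beyond doubt. Rewording would cost almost nothing.

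Part of this stands. The sums are right, the Research Plan sentence is incomplete, and the protocol does not say in so many words that 25 is a ceiling.

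The rest is weaker.

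- No section assigns 3 patients to each of the other sites. Three is the lower end of a planning range, and the sentence that follows it in Section V.12 disclaims any minimum. One could argue that the disclaimer concerns only the total, but even then nothing turns the range into a floor that every site must reach.
- Section V.5 says that 5 per site can be tested, which is permission and not a quota. An allowance per site above the average needed is an ordinary way to let quicker sites make up for slower ones, and it does not contradict a lower overall target. Section V.3 also has Yale number every subject centrally as data forms arrive, so the lead site holds a running count against 25.
- A site that stops at 2 still has its first-subject document review. The central investigator reviews adverse events within 1 day of receiving each form and again on completion of every subject (Section V.11). Only an additional document check goes untriggered.
- Section V.11 leaves the committee to set its own review plan and stopping rules in the first week. Writing a subject number into the protocol would put down in advance a detail that the committee can settle.

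**Conclusion.** No change follows. What remains is a clerical omission of 'per site' in the Research Plan and a mismatch of one patient (26 against 25) between planning targets. The mismatch appears only if the lower end of the per-site range is treated as binding at all seven other sites while Yale fills its 5.

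The study tests no hypothesis, so power and error rates are not in play. The occlusion and ease-of-use results are descriptive, and one patient more or fewer at one site would not alter how they are read. The half-way safety review is at the 13th subject on either total.

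This conclusion rests on two readings, both supported by the text: that 25 is the intended overall number, since it is stated twice and identically, and that 5 per site is an upper allowance within it. It would need to be revisited only if enrolment were in fact run towards 40, which no section proposes.
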